4.3.2 Analysis

All patients who have completed the baseline observation period and have received at least one dose of CBZ will be included in the primary analysis.

Height measurements will be displayed graphically by individual indicating measurements taken during baseline and treatment periods.

Height measurement data will be analysed using the STATA commend **xtgee** to estimate the parameters of the regression model in 4.3.1. The parameter β_3 representing the change in growth velocity will be reported together with 95% confidence interval. The Huber/White/sandwich estimator of variance will be used to obtain confidence intervals [in STATA: vce(robust)].

If fitting the growth model in section 4.3.1 is problematic, for example, lack of convergence, then a simplified analysis will be considered.

For subject *i* (*i* = 1,..,*N*), let v_{ik} denote growth velocity (a continuous response variable) measured during the baseline period (*k*=1) and the treatment period (*k*=2). Growth velocity during the baseline period for each participant will be estimated using the first available and last available measurement during the baseline period; the growth velocity during the treatment period will be estimated in a similar manner.

The model for growth velocity is:

$$v_{ik} = \beta_1 + \beta_{2i} + \beta_3 P_k + \varepsilon_{ik},$$

where β_1 , β_{2i} and β_3 are regression parameters to be estimated using simple linear regression. P_k takes the value 0 for baseline period velocities (*k*=1) and 1 for treatment period velocities (*k*=2). As for the previous GEE model, the parameter β_3 represents the change in growth velocity between treatment and baseline periods. The parameter β_3 representing the change in growth velocity will be reported together with 95% confidence interval.

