2.6 Sample size and power

The sample size was chosen on the basis of the feasible number of patients that could be recruited to the trial in the specified time period. No statistical criteria were used to choose the sample size.

The trial was initially designed to have a cohort of 12 participants in Stage 1, the dose determination stage, and a cohort of 28 participants in the treatment stage, Stage 2. However due to the COVID-19 pandemic delays, this has been amended to Stage 1; N=11 and Stage 2; N=29. The overall sample size remains the same (N=40)

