4.3.1 Statistical model for growth

For subject *i* (*i* = 1,..,*N*), let τ_{ij} be a treatment indicator taking the value 0 for measurements observed during the baseline period and 1 for measurements observed during the treatment period; treatment for individual *i* starts at time T_i .

Let y_{ij} denote a continuous response variable (e.g., height), observed at measurement times t_{ij} (j = 1,.., n_i), the model for which is:

$$y_{ij} = \beta_1 + \beta_2 t_{ij} + \beta_3 \tau_{ij} (t_{ij} - T_i) + \varepsilon_{ij},$$

where β_1 , β_2 and β_3 are regression parameters to be estimated using Generalised Estimating Equations (GEE). The "working" correlation matrix is given by,

$$Corr(\varepsilon_{ij}, \varepsilon_{ij'}) = \begin{cases} 1 & if \ j = j' \\ \rho & otherwise \end{cases}$$

This is sometimes referred to as an exchangeable covariance model. The first observation on each individual, y_{i1} , takes place at time t_{i1} =0.

- During the baseline period, $y_{ij} = \beta_1 + \beta_2 t_{ij} + \varepsilon_{ij}$.
- At the start of the treatment period, $y_{ij} = \beta_1 + \beta_2 T_i + \varepsilon_{ij}$.
- During the treatment period, $y_{ij} = (\beta_1 \beta_3 T_i) + (\beta_2 + \beta_3)t_{ij} + \varepsilon_{ij}$.

The parameter β_3 represents the change in slope between the baseline and treatment periods, i.e., the change in growth velocity.

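### The SAP's 95% intervals use an uncorrected sandwich variance with at most 40 children and very unequal follow-up, so they are probably somewhat too narrow (about 89-94% coverage under assumed variance components)

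*SAP*

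**What the plan says.** SAP 4.3.1 models height with a common intercept, a slope on time (beta2) and a change in slope from the start of treatment (beta3). The model is fitted by GEE with equal correlation between any two visits of the same child: "This is sometimes referred to as an exchangeable covariance model".

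Under SAP 4.3.2, beta3, "representing the change in growth velocity will be reported together with 95% confidence interval". The variance method is fixed: "The Huber/White/sandwich estimator of variance will be used to obtain confidence intervals", with xtgee and vce(robust) named. The analysis set is broad: "All patients who have completed the baseline observation period and have received at least one dose of CBZ will be included in the primary analysis".

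SAP 4.3.4 repeats the primary analysis in children prescribed at least 15 mg/kg on average over their first 12 months. SAP 4.4.2 uses the same variance estimator for the secondary outcomes, and the adjusted models in 4.3.3 extend the primary model.

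On numbers, SAP 2.6 says "this has been amended to Stage 1; N=11 and Stage 2; N=29" and "No statistical criteria were used to choose the sample size". The simplified analysis in 4.3.2 is reserved for trouble in fitting the GEE, such as non-convergence. Neither document mentions a bias-corrected variance, a t reference distribution or a bootstrap.

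**The concern.** The sandwich estimator is consistent as the number of clusters grows, and here a cluster is a child. With few children two things go wrong. Fitted residuals are smaller than true errors, so the estimated variance is too low on average. The estimate is also itself noisy, which a normal quantile of 1.96 ignores.

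Both effects grow when a few clusters dominate the fit. Beta3 is a slope contrast, so a child with 12-18 months of baseline and up to 36 months of treatment has far more influence than one with 6 and 12. There are at most 11 children of the first kind.

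There is no control arm, and the sample size was not set for precision. The interval for beta3 is therefore the main quantitative basis for judging whether efficacy warrants a development programme (SAP 1.3.1 and 4.3). If it is too narrow, the evidence looks firmer than it is.

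**Working it through.** **What can be reproduced.** The plan gives no power or precision calculation. The only sum to check is 11 + 29 = 40, which is right. The figure at issue is the nominal 95% level.

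**Inputs from the documents.**
- Baseline: 12-18 months in Stage 1, some children without a 6-month visit (protocol 5.1); 6 months in Stage 2.
- Treatment: 24 months in Stage 1, optionally 36; 12 months in Stage 2 (protocol Table 4, SAP 2.5.1 and 2.7).
- Model and working correlation: SAP 4.3.1. Variance: SAP 4.3.2.

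**Assumptions not in the documents.** Main set: SD of velocity 1.0 cm/yr, SD of change in velocity 0.5 cm/yr, error SD 0.3 cm (between-child height SD 12 cm in runs B and C below). Wider set: height SD 10-15 cm, velocity and change SDs 0-2 cm/yr, error SD 0.3-0.5 cm, normal or t4 child effects. Growth is otherwise linear, as the SAP assumes.

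**Formulas.** With B = sum of X_i'W_iX_i and residual vector e_i for child i:
- Plan: V = B^-1 [sum of X_i'W_i e_i e_i' W_iX_i] B^-1, interval beta3 ± 1.96 × SE.
- Mancl-DeRouen: replace e_i by (I - H_i)^-1 e_i, where H_i = X_i B^-1 X_i'W_i, interval beta3 ± t(N-3) × SE.

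H_i is the leverage of child i and is largest for the long-follow-up Stage 1 children.

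**Coverage of the plan's interval, main assumptions** (run A 4,000 trials per setting, B and C 1,500; Monte Carlo SE about 0.4-0.9 points):

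| Stage 1 + Stage 2 children | Stage 1 treatment data | A | B | C |
|---|---|---|---|---|
| 11 + 29 | to 12 months | 93.3% | - | 93.1% |
| 11 + 29 | to 24 months | 92.6% | 92.7% | 91.7% |
| 11 + 29 | about half to 36 | 90.1% | 91.0% | 89.4% |
| 11 + 29 | all to 36 | 93.1% | 93.5% | - |
| 8 + 17 (size assumed) | about half to 36 | 87.9% | 88.8% | - |
| 6 + 14 (size assumed) | about half to 36 | 86.5% | 84.5% | 85.4% |

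**Wider assumptions** (2,000-3,000 trials per setting): 89-94% with 40 children, most settings 90-93%; 85-91% with 24; 85-93% with 20. Applying the factor N/(N-1) to the variance moved coverage by at most about one point.

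**How much is bias in the SE?** If the SE were only too small by a ratio r, coverage would be 2Φ(1.96r) - 1.
- 40 children, half extended (run B): r = 0.338/0.362 = 0.934; 1.96 × 0.934 = 1.83; coverage 93.3%. Simulated: 91.0%.
- 20 children, half extended (run B): r = 0.439/0.532 = 0.825; 1.96 × 0.825 = 1.62; coverage 89.4%. Simulated: 84.5%.

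The average SE is too small, and the rest of the loss is consistent with the noise in the SE. That is why the bias correction and the t quantile are both needed.

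**Number of children or unequal follow-up?** With 40 or 20 children all on the Stage 2 schedule, coverage was 93-94%. With 6 + 14 children cut at 12 months it was 91.3%, against 85.4% with the longer data. Leverage of the long Stage 1 records drives much of the loss. It is worst when only about half are extended, so that the weight falls on about five children.

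**Who enters the dose-restricted subset.** Under the weekly titration in SAP 3.1.6:
- A child who stops at 15 mg/kg averages (7×5 + 7×10 + 351×15)/365 = 5370/365 = 14.7 mg/kg, below the cut-off.
- A child who reaches 20 mg/kg on schedule averages (7×5 + 7×10 + 7×15 + 344×20)/365 = 7090/365 = 19.4 mg/kg, well above it.

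The subset size therefore turns on how many children reached the full dose, which the documents do not say.

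**After correction** (Mancl-DeRouen, t on N-3): about 93-96% with 40 children and 92-97% with 20-24.

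**The case against.** **The loss may be small.** The endpoint is defined over 12 months, and protocol 8.8.7 takes the Stage 1 endpoint at the end of dose titration. If Stage 1 data are cut there, coverage is about 93%. With velocity SD 0.5 cm/yr as well, one run of 1,000 trials gave 95.0%, no deficit at all. This stands, and it is why a range is given. But SAP 4.3.2 states no cut, and SAP 4.3.4, which repeats the primary analysis, keeps growth data from extended treatment. The number extended is not given, and protocol 8.8.7 limits the option to UK Stage 1 children who started before 2 March 2021.

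**The subset may be nearly the full set.** The IDMC agreed 20 mg/kg for Stage 2 (SAP 1.2), and a child titrated to it on schedule passes the cut-off easily. A reader might infer that the sensitivity analysis covers only 86-88%. The documents do not support that as a property of the plan: the figure needs an assumed subset of about 20-25 children.

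**No decision rule is breached.** There is no test, alpha or go/no-go threshold, and protocol 2.3 describes initial data to inform a later randomised trial. A reader might infer a false-positive rate of 7-10% for the decision. What the plan supports is narrower: an interval labelled 95% that covers less.

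**The correction is not perfect.** With 5 of 11 Stage 1 children extended and a change SD of 1-2 cm/yr, one set of runs reached only 91.4-92.4% after correction. It reduces the shortfall rather than guaranteeing 95%.

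**Conclusion.** The point holds at moderate size. As written, the SAP's 95% intervals are likely to be too narrow. For beta3 with 40 children, coverage is about 89-94%: about 93% if Stage 1 data stop at 12 months, about 89-91% if about half of the Stage 1 children contribute 36 months. With a subset of only 20-24 children it would be about 85-93%. The direction is well supported; the figures rest on variance components, extension numbers and a subset size that the documents do not give.

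Two further inferences should be resisted. The cause is not the number of children alone, since equal follow-up would cost only one or two points. And the beta3 interval is not the trial's only inferential statement: 4.4.2 reports further 95% intervals, and 4.3.3 and 4.3.4 rerun the growth model. The 4.4.2 model, with its fourth parameter and questionnaire scores, was not simulated, so the point extends there by analogy.

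The simulations isolate variance estimation. Bias from age-related change in growth velocity is a separate matter.

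**What to change.** In SAP 4.3.2, 4.3.4 and 4.4.2, and in the 4.3.3 models that inherit the method, replace the plain sandwich by a bias-corrected one such as Mancl-DeRouen. Use t quantiles on N minus the number of mean parameters: N-3 for the growth model, N-4 for the models in 4.3.3 and 4.4.2. With 40 children the growth-model multiplier becomes t(37) = 2.03 instead of 1.96; with 20 it becomes t(17) = 2.11. Report beside each interval the number of children and their length of follow-up, because coverage depends on both.

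No new data, visits or change of estimand are needed. The cost is SAP wording, some programming beyond the vce(robust) option that the SAP names, and wider intervals. On one simulated data set of 40 children the SE rose from 0.577 to 0.660; with the t quantile the interval widened by (0.660/0.577) × (2.026/1.960) = 1.18, or about 18%. The widening will vary with how many Stage 1 children have long follow-up.

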4.3.3 Secondary analysis of primary outcome

4.3.3.1 Surgical interventions

Surgical interventions are recorded throughout the baseline and treatment periods for all participants. Following completion of the trial a review will be conducted by the CI to assess whether any of the surgical interventions could have the potential to affect growth. In the event that some interventions are thought to have potentially affected growth, the primary analysis will be repeated using an extension to the primary analysis model which allows the growth rate to change following surgery.

Let δ_{ij} be an indicator variable taking the value 0 for measurements observed before time T_i^* and 1 for measurements observed after time T_i^* , where T_i^* denotes the time of the surgical intervention for participant *i*.

The model used to adjust for surgical interventions is then given by:

$$y_{ij} = \beta_1 + \beta_2 t_{ij} + \beta_3 \tau_{ij} (t_{ij} - T_i) + \beta_4 \delta_{ij} (t_{ij} - T_i^*) + \varepsilon_{ij}$$

Before the surgical intervention the model remains unchanged from the model used in the primary analysis, however after the surgical intervention, the model becomes

$$y_{ij} = (\beta_1 - \beta_4 T_i^*) + (\beta_2 + \beta_4)t_{ij} + \beta_3 \tau_{ij} (t_{ij} - T_i) + \varepsilon_{ij}$$

and so allows for a change in growth rate from the point of surgery onwards. The change in growth rate is estimated by the parameter β_4 .

4.3.3.2 25-OH Vitamin D

25-OH vitamin D levels might predict secondary effects on bone health and could be considered a potential confounding variable. Bone biochemistry bloods (25-OHD vitamin D [nmol/L]) are recorded 6 monthly throughout the trial. 25-OH vitamin D levels will be included as a time-varying covariate in the primary analysis model to adjust for any effects of vitamin D level. A last observation carried forward approach will be taken to impute vitamin D levels when missing.

Let z_{ij} be the standardised 25-OH vitamin D level for participant *i* at time t_{ij} (j = 1,..., n_i),

i.e. $z_{ij} = (x_{ij} - \bar{x})/\sigma_x^2$, where x_{ij} is the observed 25-OH vitamin D level, and \bar{x} and σ_x^2 are the sample mean and variance of all 25-OH vitamin D observations across all participants.

The model used to adjust for the effect of vitamin D is given by:

$$y_{ij} = \beta_1 + \beta_2 t_{ij} + \beta_3 \tau_{ij} (t_{ij} - T_i) + \beta_4 z_{ij} t_{ij} + \varepsilon_{ij}.$$

This can be written as:

$$y_{ij} = \beta_1 + (\beta_2 + \beta_4 z_{ij})t_{ij} + \beta_3 \tau_{ij}(t_{ij} - T_i) + \varepsilon_{ij}$$

which makes clear how the time varying covariate, 25-OH vitamin D, affects the rate of growth.

4.3.4 Sensitivity analysis of primary outcome

The primary analysis will be repeated including only those participants who have completed their baseline observation period and have been prescribed, on average, at least 15 mg/kg of CBZ over their first 12 - months of treatment, i.e. a dose which is at least 75% of the dose recommended from Stage 1.

Note that some participants will have longer than 12 months of treatment. Dosing details during these extended periods of treatment will not be considered when determining if a participant is included in this sensitivity analysis. However, if a participant is included, then the participant's growth data for this extended period of treatment will be included in the analysis.

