8.8.7 Continuation of treatment with CBZ for Stage 1 participants

Assuming Stage 1 participants have achieved their MTD and no significant safety concerns arise from the dose titration 6 month safety review, participants from Stage 1 will continue treatment with CBZ. They will receive the dose approved by the trial IDMC until they have received 24 months of IMP treatment (post initiation of IMP treatment) to allow their data to be included in the Stage 2 final analysis. If a participant has not reached the dose approved by the trial IDMC, they will continue on the maximum dose they were able to tolerate until they have received 24 months of IMP. Stage 1 participants will continue to attend trial visits every three months as indicated in the schedule of events –treatment (Table 7) and the participant visit schedule (Table 4). Eligible Stage 1 participants in the UK, who commenced treatment before 2nd March 2021, will have the option to continue treatment with CBZ for an additional 12 months after they have completed 24 months of IMP treatment. All trial visits must be completed by 31st January 2024.

Assuming the dose regimen is sufficiently similar in stage 1 and 2, stage 1 patients will be included in the analysis at the end of the trial, using the primary endpoint measured at the end of the dose titration phase for stage 1 and at the end of 12 months of treatment for stage 2. If the dose regimen changes between stage 1 and stage 2, we will consult with the IDMC as to whether stage 1 and stage 2 patients should be combined in the final analysis.

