2.4 Definition of outcome measures

2.4.1.1 Primary objectives/endpoints

	Objective	Outcome
Primary	To evaluate efficacy of CBZ for the treatment of children with MCDS who are ambulant but have not yet reached skeletal maturity (open epiphyses)	Alteration from baseline in growth velocity over 12 months
	To determine if the level of efficacy warrants a subsequent formal development programme for CBZ in this indication.	Growth velocity follow-up data at 12 months post treatment initiation

Participants undergo an observational phase (12-18 months for Stage 1 participants; 6 months for Stage 2 participants) prior to starting treatment. Measurements taken include data on height and weight. The same measurements are taken at various time points during the treatment period, allowing an assessment of growth velocity and any change which might be due to treatment.

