2.7 Overview of MCDS-Therapy Clinical Trial (from Protocol)

*The 12 month baseline observational visit may be rescheduled to a 18 month visit for participants who have missed the 12 month visit due to COVID-19 (Stage 1 UK participants only).

[^] To aid with study participant retention due to COVID 19, with discussion with the CI, the 12 month baseline observational visit window can be up to 12 months and 8 weeks. This will be assessed on a case by case basis through discussion with the site PI^a with approval from the CI and the NCTU team notified.

Eligible Stage 1 participants may continue treatment for further 12 months (up to 36 months) subject to a separate informed consent at visit 2.5.

Last Patient Last Visits in Stage 1 and Stage 2 must be completed by 31st January 2024.

3 Study Population

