4.2 Analysis populations

There will be two analysis populations:

1. Participants who have completed the baseline observation period and have received at least one dose of CBZ.

2. Participants who have completed their baseline observation period and have been prescribed, on average, at least 15 mg/kg of CBZ over their first 12 -months of treatment, i.e. a dose which is at least 75% of the dose recommended from Stage 1. Note that some participants will have longer than 12 months of treatment.

Adverse events will be reported for all participants who start their baseline period.

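### The primary outcome is a 12-month change in growth velocity, but the SAP sets no limit on treatment time, so by implication 24 to 36 months of Stage 1 heights enter the primary estimate beside 12 months for Stage 2

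*SAP*

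**What the plan says.** The outcome is "Alteration from baseline in growth velocity over 12 months" (SAP 2.4.1.1; Protocol section 4 gives the same time frame). Because the dose regimen did not change, SAP 2.1 includes Stage 1 children in the Stage 2 analysis.

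The two stages have different treatment periods. Stage 2 children are treated for 12 months. Stage 1 children are treated for 24 months, with an optional further 12 under separate consent. SAP 4.2 acknowledges this: "Note that some participants will have longer than 12 months of treatment".

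SAP 4.3.1 sets the treatment indicator to 1 for every height in the treatment period, and SAP 4.3.2 names no cut-off. The fallback velocity runs from the first to the last available height in each period. SAP 4.3.4 repeats the primary analysis in children with an adequate average prescribed dose over their first 12 months. It disregards dosing after that point but states that "growth data for this extended period of treatment will be included in the analysis".

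The protocol points both ways. One sentence of Protocol 8.8.7 brings Stage 1 into the final analysis "using the primary endpoint measured at the end of the dose titration phase for stage 1 and at the end of 12 months", where the second time point is the one for Stage 2; both fall at 12 months on treatment. Another sentence of 8.8.7 keeps Stage 1 children on treatment to 24 months so that their data can enter the final analysis, and Protocol 5.2 foresees their 12- and 24-month data there.

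**The concern.** β3 is the one estimate on which the primary objective rests; it "will be reported together with 95% confidence interval", and there is no control arm. If the heights run to 24 or 36 months in one stage and 12 in the other, β3 is no longer the stated 12-month outcome. It becomes a mixture whose weights depend on how long each Stage 1 child stayed on treatment.

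The primary model has no term for age or puberty and takes growth as linear within each period. The longer the treatment period, the further its average age lies from that of the baseline period, and the more any natural change in velocity is counted as a drug effect. If velocity falls with age, a useful drug could look ineffective. In a pubertal spurt, an inactive one could look useful.

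**Working it through.** There is no planned figure to reproduce: "No statistical criteria were used to choose the sample size" (SAP 2.6).

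**Inputs**
- Children: 11 in Stage 1 and 29 in Stage 2 (SAP 2.6), so Stage 1 is 11/40 = 27.5%.
- Heights (Protocol Table 4 and the schedules of events): Stage 1 baseline at 0, 6 and 12 months, then every 3 months on treatment to 12, 24 or 36. Stage 2 baseline at 0 and 6 months, then every 3 months to 12.
- Model: SAP 4.3.1, exchangeable correlation. The documents give no ρ; 0.5, 0.9 and 0.99 are assumed.
- Natural slowing: the documents give no growth rates. An assumed fall of d cm/yr per year adds -d·t²/2 to height, with t counted from the first baseline visit. The drug effect is set to zero.

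**Share of heights after treatment start.** Stage 2 contributes 29 × 4 = 116.
- 12 months: 44/(44 + 116) = 27.5%
- 24 months: 88/(88 + 116) = 43%
- 36 months: 132/(132 + 116) = 53%

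**Share of information on β3.** With A = Σ Xᵢ'V⁻¹Xᵢ over all children and c = (0, 0, 1), the Stage 1 share is the Stage 1 sum of c'A⁻¹Xᵢ'V⁻¹XᵢA⁻¹c divided by c'A⁻¹c. The expected β3 with no drug effect is the third element of A⁻¹ Σ Xᵢ'V⁻¹mᵢ, where m = -t²/2 for d = 1. Ranges are over ρ.

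| Stage 1 treatment heights to | Stage 1 share of β3 | Spurious β3 for d = 1 (cm/yr) |
|---|---|---|
| 12 months | 48-49% | -0.6 to -0.7 |
| 24 months | 66-67% | -1.5 to -1.6 |
| 36 months for 5, 24 for 6 | 69-70% | -2.2 to -2.3 |
| 36 months for all 11 | about 70% | -2.6 to -2.7 |

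Stage 1 already holds nearly half at 12 months because its baseline is twice as long.

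**Sensitivity to the set-up.** The figures above give both stages the same velocity at the first baseline visit. Aligning them at treatment start instead gives -1.0, -1.5 and -2.5 at 12, 24 and 36 months (ρ = 0.9). With an 18-month baseline for all Stage 1 children, the 24-month share is 75-77% and the bias -1.2 to -1.4. The order is the same throughout.

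**Fallback.** With first and last heights, the bias for d = 1 is minus the gap between period midpoints, each child counting equally. The gap is 1.0, 1.5 or 2.0 years for Stage 1 (12, 24, 36 months) and 0.75 for Stage 2.
- 12 months: (11 × 1.0 + 29 × 0.75)/40 = 0.82
- 24 months: (11 × 1.5 + 29 × 0.75)/40 = 0.96
- 36 months: (11 × 2.0 + 29 × 0.75)/40 = 1.09

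**Effect on the interval.** Three hundred trials per setting were simulated with robust GEE and no drug effect. Assumed values were ages 3-11, velocity 5 cm/yr at age 7, between-child velocity SD 0.7 cm/yr and measurement SD 0.3 cm.

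| d | Mean β3 at 12 / 24 / 36 months | 95% interval covers zero |
|---|---|---|
| 0 | -0.01 / -0.01 / 0.00 | 93% / 93% / 93% |
| 0.1 | -0.08 / -0.16 / -0.25 | 91% / 71% / 67% |
| 0.25 | -0.19 / -0.38 / -0.68 | 85% / 18% / 11% |
| 0.5 | -0.36 / -0.79 / -1.38 | 77% / 1% / 1% |

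**The case against.** The SAP may have kept the extended heights on purpose: in a rare disease with a sample set by feasibility, each height counts. With no natural slowing, longer follow-up brings no bias and some precision; the simulated SD of β3 was 0.22 at 12 months, 0.13 at 24 and 0.17 at 36. That stands as a cost of any cut. It does not make the estimate the stated 12-month outcome.

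The inclusion sentence sits in the sensitivity analysis, so its application to the primary analysis is an inference. It is a strong one: 4.3.4 repeats the primary analysis and 4.3.2 sets no window.

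The height z-score model (SAP 2.4.1.2.1 and 4.4.2) standardises for age and sex and so meets part of the ageing problem. It is a secondary analysis, and it reuses the same unlimited treatment indicator.

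Four stronger readings are tempting but not supported:
- **That the SAP breaks a clear 12-month protocol rule.** Protocol 5.2 and part of 8.8.7 foresee 24-month Stage 1 data, so the documents are unreconciled. Neither passage, however, provides for 36-month heights in a 12-month outcome.
- **That Stage 1 supplies 87% of the evidence.** That is its share of the treatment-period sum of squares at 36 months: 11 × 11.375/(11 × 11.375 + 29 × 0.625) = 0.87. It does not apply to β3. Nor does a 12-month cut restore a 27.5% share of β3.
- **That self-selected extension children hold most of the information.** Months 12 to 24 are scheduled treatment. Going on to 36 raises the β3 share only from 66-67% to about 70%.
- **That all 11 reach 36 months.** Extension is optional and limited to children who started before 2 March 2021. With last visits by 31 January 2024, a full 36 months needs a start by about 31 January 2021. The number extending is not given.

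**Conclusion.** The point holds. The stated outcome covers 12 months, and the planned analysis, by its lack of a window and by 4.3.4, covers up to 24 or 36 months for Stage 1. The shares follow from the visit schedule and the assumed ρ; the 24-month share does not depend on who extends, and the 36-month figure is a ceiling.

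The bias figures are conditional. They assume steady slowing that the documents neither give nor rule out, and they scale with it: at 0.25 instead of 1 cm/yr per year, each is a quarter as large. The direction is against the drug if growth slows and could favour it in a pubertal spurt. The fallback moves only modestly, from -0.82 to -0.96 or -1.09.

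**What to change.** State in SAP 4.3.2 and 4.3.4 that the primary, fallback and sensitivity analyses use heights up to and including the 12-month treatment visit with its window: visit 1.6/2.1 for Stage 1 and visit 2.5 for Stage 2. Put later Stage 1 heights in a labelled supportive analysis. Reconcile Protocol 5.2 and 8.8.7 with SAP 2.4.1.1 and 4.3.4, so that one window is stated throughout.

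The cost is a short SAP change, a data filter and the protocol reconciliation. Later Stage 1 heights leave the primary estimate, with the loss of precision noted above. The cut reduces the ageing bias but does not remove it: at d = 0.25 the simulated interval still covers zero only 85% of the time. An adjustment for age, or the height z-score result shown beside β3 under the same window, would address what remains.
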